### **3.9 Location**

The University of Chicago CCD recovery room. This facility is outfitted with all the necessary emergency and equipment required to maximize safety. The isolation recovery room that we use is perfect for our purposes since it is soundproof.

### **3.10 Payment to Subjects**

\$500 will be given to each subject for every day they are anesthetized. \$1000 will be provided to each subject for completing the entire trial. Since the subjects will be in the trial for 2 full days, the payments reflect an average salary for a working day of \$500/day. The subject will receive \$500 after each anesthesia session.

### **3.11 Informed Consent Process**

One of the anesthesiologists will provide a verbal explanation of the study to the subject and answer all questions regarding this study. Then, a written description of the study will be provided to the subject. Afterwards the subject will be required to describe the study in their own words showing that they understand the purpose of the study, the risks involved and their own role in the study. If any risks are not well understood, the members of our team will explain them, in detail. The subject and the person who administered the informed consent must sign and date the document. A copy of the informed consent form will be given to the subject and the original will be kept in the subject's record.

### **3.12 Subject Withdrawal Following Study Completion**

The final "anesthesia" visit will be no different than the previous one. After the subject wakes from anesthesia and completes the psychomotor tests, he will be released to home, in company with another adult, once he meets the safety criteria for release. This will be followed up by phone calls for the subsequent 2 weeks to ensure that the subject has not suffered any adverse effects from the treatment.

All subjects will be asked, upon completion of the study, to help us identify ways to make the study better. The idea for combining the informed consent and the history and physical sessions arose from complaints from test subjects.

### **3.13 Subject Withdrawal Before Study Completion (i.e., early termination)**

All subjects are free to withdraw from participation in the trial at any time, for any reason, specified or unspecified, and without prejudice.

Not uncommon side effects of anesthesia are nausea and vomiting, mild to moderate sore throat, transient hypoxia (low oxygen level), transient blood pressure and heart rate changes (sinus arrhythmia). Most people do not experience any of these events. They are reversible and have no long-term consequence. But they can be unpleasant to the volunteer. Thus, the volunteers may decide not to complete the 2 rounds of anesthesia. Our expectation is that there will be significant drop out.

If there is a more serious event associated with the trial, then the IRB will be informed immediately and the subject will be monitored until the issue is resolved.

If we observe that the subject does not easily tolerate anesthesia, as indicated by changes in vital signs, or alternatively if the toxicology screen comes back positive for drugs or alcohol or alternatively if the subject does not bring a responsible adult with him to the session, they will be asked to leave the trial. Termination will have no adverse health consequences, but if the subject had previously received anesthesia there will be follow-up phone calls identical to those received by subjects who complete the trial.

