### **2.2 Duration of Study**

Screening: 1 week

Intervention: 6 weeks total

Follow-up: 2 weeks

Part 1: We will enroll up to 8 test subjects in a full scale trial. The estimated duration of this trial will be approximately 16 weeks followed by a 2 week follow up period.

Week 1: Explanation of the trial and signature of informed consent form. Detailed medical exam and physical exam. Toxicology screen and acceptance into trial. Training with psychomotor tests.

Week 2: Volunteers will be exposed to isoflurane anesthesia as described below and then receive and injection of either a saline solution or caffeine citrate (both investigators and subjects will be blind to composition of injection). Psychomotor tests will be carried out. There will be a toxicology screen. Later that day and then the day after the session, there will be a telephone follow-up with the subject.

Week 3: There will be a telephone follow-up with both volunteers.

Week 4-6: Volunteers will be exposed to isoflurane anesthesia as described below and then receive and injection of either a saline solution or Caffeine (both investigators and subjects will be blind to composition of injection). Psychomotor tests will be carried out. There will be a toxicology screen. Later that day and then the day after the session, there will be a telephone follow-up with the subject.

Weeks 6: There will be telephone follow-ups with both volunteers.

Week 7: There will be a final series of telephone follow-up with both volunteers. If there are no issues identified, this will be the last contact with the volunteers.

We are suggesting that the trial take place over 16 weeks due to scheduling conflicts i.e. the possibility that subjects are not available. We hope to anesthetize 2 subjects per single lab day.

We are asking to be allowed to enroll up to 8 additional volunteers, but we will only require 6-8 to complete the study. If we need additional subjects due to dropout from the trial, we will ask the IRB for additional subjects. After 6 subjects are completed we will submit a continuing review after enrolling 6 additional subjects in order to inform the IRB of the study progress, how subjects tolerated the dosing changes, and if there were any subject safety issues.

If we are given IRB approval, the next set of test subjects will take 4-6 weeks to complete the trial. There will also be a two week follow-up period.

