## **2.9 Primary Safety Endpoints**

Throughout each anesthesia visit, the subject's vital signs will be monitored and there will be two experienced anesthesiologists present throughout the anesthesia session. Both anesthesiologists will be present for the first hour of the recovery time following the anesthesia. Once the test subject is awake, oriented with regards to time and space, and showing stable vital signs, typically about an hour after terminating the isoflurane, one of the anesthesiologists may leave the room. There will be one anesthesiologist present at all times until the subject is discharged.

At the conclusion of each "anesthesia" visit, we will discharge the subject based on the criteria used in our post anesthesia care unit in the hospitals. In general, the subject should be awake and alert with the stable vital signs. He should be able to drink clear liquid, void and ambulate before discharge home. We will call a car service for him without cost to the subject. The subject will be expected to live within 30 miles of The University of Chicago to make sessions easily accessible. Upon discharge from the

hospital, the subject will be required to be accompanied by a responsible adult. Each session for any given subject will be at least 2 weeks apart. The total time of each session, including the pre-anesthesia preparation, testing and recovery from anesthesia, will be ~4 hours. We will call the subject later the same day and then again the next day to make sure the subject fully recovers without any adverse event. The subject will get another call a week after the procedure. In some cases we may use emails or text messages rather than phone calls.

After the 2nd and final anesthesia session the subject will receive phone calls for the next two weeks to ensure complete recovery and no adverse effects.

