### **3. SUBJECT SELECTION AND WITHDRAWAL**

#### **3.1 Number of Subjects**

For this study of up to 8 subjects will be tested. There will be a progress report to the IRB after 6 subjects.

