#### **4.4A Subject Compliance Monitoring**

Compliance will be monitored with a toxicology screen. Data from the screen will be included in the study database containing recovery from anesthesia data. Any subjects that do not meet compliance guidelines (no drugs or alcohol) will be asked to leave the study. If they do not bring a responsible adult to the anesthesia sessions they will be asked to leave.

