### **6.3 Subject Population(s) for Analysis**

The data from all subjects will be analyzed without knowledge of whether the data comes from a control or test condition. After breaking the code, data will be grouped accordingly. All data will be analyzed in two different ways. Using a paired t-test data from subjects that have completed the two anesthesia sessions of the study will be analyzed and plotted. Separately, using an unpaired t-test all data will be grouped together including that from subjects who did not finish the trial. In this way the data will be compared. Only data from subjects that failed the toxicology screen will be excluded.

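### A man who comes to session 2 without an escort must leave the trial, with no provision to rebook, so the paired t-test loses his pair

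*Combined protocol and SAP*

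**What the plan says.** The rule appears twice. Section 3.13 states that "if the subject does not bring a responsible adult with him to the session, they will be asked to leave the trial". It stands in the same sentence as a positive toxicology screen and poor tolerance of anesthesia, with the same consequence. The next sentence calls this termination and foresees that the man may already have been anesthetized, in which case he gets the usual follow-up calls. Section 4.4A, on compliance, says: "If they do not bring a responsible adult to the anesthesia sessions they will be asked to leave". Neither section separates session 1 from session 2, and neither mentions another date.

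The escort is tied to going home. Under Section 2.9, on discharge "the subject will be required to be accompanied by a responsible adult"; Sections 3.12 and 5.2 say the same.

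On numbers, Section 3.1 says "For this study of up to 8 subjects will be tested". Section 2.2 adds "we will only require 6-8 to complete the study" and "If we need additional subjects due to dropout from the trial, we will ask the IRB for additional subjects". Section 3.13 expects considerable dropout but gives no rate.

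On analysis, Section 6.3 plans two comparisons. The first is restricted to completers: "Using a paired t-test data from subjects that have completed the two anesthesia sessions of the study will be analyzed and plotted". The second is an unpaired t-test on all data, including men who did not finish. Only data from failed toxicology screens are excluded.

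On time, Section 2.2 says "We are suggesting that the trial take place over 16 weeks due to scheduling conflicts i.e. the possibility that subjects are not available", and then asks for up to 26 weeks to cover dropouts. Section 2.3 sets a 2-week minimum between sessions. The Study Summary puts each man on study for up to 10 weeks.

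**The concern.** The consequence goes further than the stated purpose of the escort needs. If a man arrives alone, not anesthetizing him that day already ensures that he is not discharged alone after anesthesia. Ending his participation as well adds nothing to that day's safety, and at session 2 it costs a pair.

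The paired t-test is the method named in the Study Summary and in Section 6.2, and it needs both sessions. Section 8.1 justifies using each man as his own control as the way to need the fewest anesthetics in total, and Section 7.2 accepts that the risks are more than minimal. Removing a man after session 1 for a logistical lapse works against that aim. Completing his pair takes one more anesthetic. Replacing it takes two in someone else, so three are given for one pair where two would have done.

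There is little margin. The plan's own calculation in Section 6.1 gives 12 people, and the plan adopts 8.

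**Working it through.** **Inputs (Section 6.1, rats).** Control mean 540 s, SD 159.04; caffeine 5 mg/kg mean 269.67 s, SD 103.69; power 95%; p ≤ 0.01. Sidedness is not stated; two-sided is assumed here. The within-subject correlation ρ is not given; 0 to 0.7 is assumed.

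**The plan's own figure first.** Difference = 540 − 269.67 = 270.33 s. Pooled SD = √[(159.04² + 103.69²)/2] = 134.25 s. Standardized effect = 270.33/134.25 = 2.01. A two-sided unpaired t-test at 0.01 reaches 95% power with 11 per condition (95.9%; 97.6% at 12). Other conventions (normal approximation or t, one- or two-sided, pooled or control SD) give 8 to 15. The stated 12 is therefore reproduced to within one.

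**Cost of a lost pair.** SD of the difference = √(159.04² + 103.69² − 2ρ × 159.04 × 103.69). Standardized paired effect dz = 270.33/SD of the difference. Power is from the noncentral t with n − 1 degrees of freedom and noncentrality dz√n, two-sided alpha 0.01.

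| ρ | SD of difference (s) | dz | 8 pairs | 7 pairs | 6 pairs | Loss, 8 to 7 (points) |
|---|---|---|---|---|---|---|
| 0 | 189.9 | 1.42 | 68.8% | 56.6% | 42.4% | 12.2 |
| 0.3 | 161.7 | 1.67 | 84.0% | 72.9% | 57.5% | 11.1 |
| 0.5 | 139.8 | 1.93 | 93.6% | 85.8% | 72.0% | 7.8 |
| 0.7 | 113.8 | 2.37 | 99.2% | 96.7% | 89.0% | 2.5 |

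The 0.01 level is a sample-size criterion; Sections 6.2 and 6.3 name no test level. At two-sided 0.05 the fall from 8 to 7 pairs is smaller: 93.0% to 87.8% at ρ = 0, and 99.6% to 98.7% at ρ = 0.5.

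**How often.** No lapse rate is given. If each of 8 men independently had probability p of lacking an escort at session 2, the chance of at least one lapse is 1 − (1 − p)⁸: 34% at p = 0.05, 57% at 0.10, 83% at 0.20. These values of p are assumptions for illustration only.

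**Is there room to rebook?** Section 2.2 puts the first anesthetic in Week 2 and the second in Weeks 4–6, a gap of 4 − 2 = 2 to 6 − 2 = 4 weeks. The schema in Section 5.2 counts from the first anesthetic as week 0 and puts the second at Week 2–4. The origins differ but the implied gap is the same. A session booked for Week 4 could move to Week 5 or 6 inside both. A later move would pass both schedules while possibly still falling within the 10-week participation period, which must also hold the two weeks of follow-up calls.

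**The case against.** The strongest reply is that nothing here is an error. Sections 3.13 and 4.4A agree with each other and with the discharge requirement. Listing the escort under compliance looks deliberate, and strict removal may deter unreliable attendance. That stands: this is a design choice that could be improved, not a contradiction. It also means that the rule cannot be called unrelated to safety. The narrower statement is that permanent removal exceeds what the discharge requirement needs.

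Several stronger readings are tempting, and the documents do not support them:

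- A reader might infer that the first anesthetic is wasted. Section 6.3 keeps those data in the unpaired analysis, so they are lost only to the paired test.
- A reader might take 8 as a hard ceiling. Section 2.2 accepts 6 to 8 completers and foresees asking the IRB for more, so one or two lost pairs stay within the plan's stated range.
- A reader might treat all of the 16 to 26 weeks as rebooking time. Only the 16 weeks are requested for scheduling conflicts; the 26 weeks are for dropouts. Both are trial-level durations, not limits for one man.
- A reader might say that rebooking is forbidden. The text is silent, though asking a man to leave and calling it termination make permanent removal the natural reading.

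The power figures also show the cost of any lost pair, whatever the cause. They rest on rat data that Section 6.1 itself says may mislead, and a rebooked man may still not return.

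**Conclusion.** The point holds as a cheap improvement. As written, a missing escort at session 2 ends participation, and the paired t-test loses a pair that could often be kept with one further visit. At two-sided 0.01 and the rat effect, one lost pair of 8 costs about 12 points of power at correlation 0, about 8 at 0.5 and 2.5 at 0.7. The loss is material unless within-subject correlation is high, and it is smaller at 0.05.

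This rests on the rat means and SDs carrying over to men and on an assumed correlation. The frequency of missing escorts is unknown, so no expected loss for the trial can be stated.

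**What to change.** In Sections 3.13 and 4.4A, replace removal for a missing escort with three statements:

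- Without a responsible adult, no anesthesia is given that day.
- The session is rebooked with its allocated treatment unchanged and the blind kept. The existing 2-week minimum gap is kept, and the new date falls within the man's own participation period (up to 10 weeks in the Study Summary).
- He leaves the trial only if he cannot attend with an escort in that period.

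Reconcile the session-2 timing in Section 2.2 and in the Section 5.2 schema with this wording, so that a rebooked session does not become a protocol deviation. The escort requirement and the toxicology rule are unchanged.

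The cost is two amended sentences and matching timing entries. For each lapse it is one extra lab slot, a discarded prepared syringe, and a longer gap between that man's sessions.

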### **3.14 Data Collection and Follow-up on Early Withdrawal Subjects**

Most people suffer no adverse effects of any sort related to anesthesia. The adverse effects that are typically experienced like sore throat or vomiting are transient in nature and subjects will have no long-term consequence. These events will be monitored by the follow-up phone calls. More serious events will be monitored closely until the event is resolved, by clinicians associated with this project or alternatively by other clinicians at UC. No follow-ups on efficacy will be carried out, as the point of the research trial is to determine whether caffeine can cause a rapid emergence from anesthesia.

We ask the IRB for approval to recruit an additional 8 volunteers.

## **4. STUDY DRUG**

### **A. Drug Study:**

#### **4.1A Formulation of Study Drug**

Caffeine citrate (caffeine), is available commercially. It is manufactured by Bedford Labs.

Placebo control will be a sterile saline solution.

#### **4.2A Treatment Regimen**

The study drug (caffeine citrate) or the placebo (a saline solution) will be given intravenously 10 min before the end of 1 hour isoflurane anesthesia. Caffeine will be administered at a dose of 15 mg/ kg. There will be a single injection of either caffeine or a saline placebo control solution in the anesthetized test subjects. The drug will be injected slowly across a 10-minute interval, in order to prevent concentration spikes in the subject. A pump infuser will be used to introduce the drug. The subjects will be told not to eat or drink for 8 hours prior to anesthesia (see below for a more detailed description).

An example of the method of administration may be illustrative. The drug, caffeine citrate and comes in a single dosage of 20 mg caffeine per ml of solution. Let's say a volunteer weighs 65 kg. The dose we propose for this trial is 15 mg/ kg. Therefore the volunteer will get a 48.75 ml injection of caffeine citrate. This amount of solution (48.75 ml) can be injected as a bolus via an IV line in under a minute. This rapid infusion of drug is what we call a bolus injection. We plan on introducing the 48.75 ml of caffeine citrate more slowly, across a 10-minute time window, to prevent spikes in the circulating caffeine concentration. The caffeine will be introduced via a pump infuser. In this case the subject will get 975 mg of caffeine citrate that is equivalent to 487.5 mg of pure caffeine.

#### **4.3A Preparation and Administration of Study Drug**

All drugs will be stored and/ or prepared by the IDS group and provided to the research team on the day of each session.

The IDS office is located in the Wyler Pavilion, room C286, but is in the process of moving to CCD. The area has equipment necessary to store, prepare, and dispense all categories and dosage forms of drugs and biologics. IDS pharmacists and technicians along with other supporting pharmacy personnel provide services to faculty, investigators, pharmacy staff, nursing staff, and subjects enrolled in research protocols. The IDS office is open up to 10 hours per day on weekdays or a staff member is on call 7 days per week. Key staff members in the central pharmacy provide dispensing support twenty-four hours a day when IDS staff is not present

Required documents for every research study are placed in designated binders. They contain sections for: Randomization schedule, Drug Accountability Records, Drug Receipt Records, Subject scripts and consent signature pages, Drug Order Forms (if applicable) or information on how to get a re-supply of drug, and any other miscellaneous forms needed. For all studies, a protocol specific procedure sheet is prepared. Each subject's order is verified with the protocol assigned and with the subject's dispensing history prior to dispensing any study medications. Discrepancies are discussed with the study nurse or physician, as appropriate. The presence of the subject's signed inform consent is verified by the pharmacist. The protocol is reviewed for all pharmaceutical information prior to attempting to prepare a study medication. A pharmacy protocol specific procedure sheet is reviewed before drug preparation is set up by the pharmacist processing the order. The Central Pharmacy area maintains all investigational drug supplies handled by the inpatient pharmacy. The IDS provides training to essential staff to provide service to protocols that require continuous service 24 hours per day, 7 days per week, and 365 days per year.

IDS maintains drug accountability records in compliance with state and federal regulations and the specific requirements of each protocol. At study termination when study drug has been either returned to the sponsor or destroyed, all drug accountability records and study-related documents are transferred to the investigator.

#### **4.4A Subject Compliance Monitoring**

Compliance will be monitored with a toxicology screen. Data from the screen will be included in the study database containing recovery from anesthesia data. Any subjects that do not meet compliance guidelines (no drugs or alcohol) will be asked to leave the study. If they do not bring a responsible adult to the anesthesia sessions they will be asked to leave.

#### **4.5A Concomitant Medications and Therapies**

Our goal is to identify a relatively young cohort of healthy volunteers. Thus patients taking drugs for chronic conditions will not be chosen.

Propofol is the preferred agent for the induction phase because it does not cause airway irritation. Isoflurane will be used as the main anesthetic agent as it is an extremely safe anesthetic that has been used for decades. During this study, we do not plan to use other anesthetic agents, such as midazolam, fentanyl, and muscle relaxants to minimize the interactions of these drugs to our study drug. However, propofol and muscle relaxants are available at the bedside in case they are needed for the management of unexpected airway situations, such as laryngeal spasm. If an unexpected airway emergency occurs, the ASA difficult airway algorithm will be applied for airway management. The subject will be allowed to breathe spontaneously unless the tidal volume is less than 3 ml/kg. We will optimize the tidal volume at around 5 ml/kg to make sure each subject receives similar amount of isoflurane for an hour. Pressure support mode may be applied to optimize the tidal volume if necessary. The study drug (caffeine citrate) or the placebo control will be given intravenously 10 min before the end of 1-hour isoflurane anesthesia. The anesthesiologists will be blinded to the medication injected to the subject since the drug or normal saline is prepared by the pharmacists in the OR pharmacy. When isoflurane is turned off, the subject will eliminate isoflurane passively via breathing.

There will be at least two anesthesiologists present during the entire period that anesthesia is administered. Each subject will be given a dose of antiemetic medication, zofran (4 mg) 20 minutes before the end of the anesthesia to minimize the incidence of post anesthesia nausea and vomiting. During the period of anesthesia, we will keep the subject's BP within 20% of its pre-anesthesia value. If the BP falls more than 20% of the baseline, we will first give IV fluid to replete the fluid deficit due to the restriction of fluid intake prior to the study. If that is not sufficient to raise the BP, we will reduce the concentrations of isoflurane by 0.1% at a time until we can maintain the BP close to the normal range. Vasoactive medications will be given only if absolutely necessary but they will be available. Volunteer safety is our first priority.

[Intraoperative hypotension is not well defined (see (Bijker *et al.*, 2007)). In clinical practice, changes of 20 - 30% of the baseline mean MP or SBP are well accepted. Transient change of BP in this range is usually clinically insignificant. Healthy volunteers tolerate these changes better than sick surgical patients. In general, lowering of blood pressure by an anesthetic is also dose dependent. Hemodynamic changes are very fluid during anesthesia. It is important not to overcorrect the minor transient change of BP and heart rate. **Nonetheless, in this trial with healthy volunteer, we will use a change of 20% from the baseline (MBP or SBP) for more than 5 min as our trigger for intervention**].

